4.2 Study Design

Study 111-206 is a phase 2 stratified randomized, double-blind, placebo-controlled clinical trial of vosoritide in infants and younger children with a diagnosis of ACH.

Subjects aged ≥ 6 months to < 60 months old who have documented ACH confirmed by genetic testing; at least a 6-month period of pretreatment growth assessment in Study 111-901 immediately before study entry; and who meet the study eligibility criteria, will participate. Eligible subjects ranging from 0 months to < 3 months old may enroll directly into 111-206 and have a minimum of 3 months of pre-treatment observation prior to commencing treatment with investigational product or may enroll in 111-901 for a minimum of 3 months of pretreatment growth assessment immediately before roll-over to 111-206.

Approximately 70 subjects will be enrolled at approximately 10-15 clinical centers worldwide.

Subjects will be enrolled into 3 age cohorts based on age at study screening starting with the eldest population. Within Cohorts 1 and 2, subjects will be stratified by age:

- Cohort 1 – children aged ≥ 24 to < 60 months ($n \geq 30$ total: 3 sentinel subjects who receive vosoritide, and at least 27 additional subjects randomized 1:1 to treatment or placebo control), stratified by age (≥ 24 months to < 36 months and ≥ 36 months to < 60 months)
- Cohort 2 – children aged ≥ 6 to < 24 months ($n \geq 20$ total: 3 sentinel subjects who receive vosoritide, and at least 17 additional subjects randomized 1:1 to treatment or placebo control), stratified by age (≥ 6 months to < 15 months and ≥ 15 months to < 24 months)

- Cohort 3 – children aged 0 to < 6 months (n ≥ 20 total: 3 sentinel subjects who receive vosoritide, and at least 17 additional subjects randomized 1:1 to treatment or placebo control). Treatment begins at ≥ 3 months to < 6 months after 3 months of observation.

[figure not shown]
Sentinel subjects from each cohort will be enrolled, treated with vosoritide, and studied for short-term safety and PK data. After the sentinel data are evaluated within a cohort additional recruited subjects will be randomized to receive vosoritide or placebo subcutaneous daily (1:1 ratio) for 52 weeks.

As subjects age on study, they will be administered the dose determined to be appropriate for their current age as follows:

All sentinel and randomized subjects in Cohort 1 received 15 µg/kg dose. Sentinel subjects in Cohort 2 initially received 15 µg/kg dose and the dose was escalated to 30 µg/kg while they remained < 24 months of age following review of PK data as per protocol. All randomized subjects in Cohort 2 will receive 30 µg/kg dose while they remained < 24 months of age. All sentinel and randomized subjects in Cohort 3 received 30 µg/kg dose while they remained < 24 months of age. The dose for all sentinel and randomized subjects in Cohorts 2 and 3 will be adjusted to 15 µg/kg/day after they turn 24 months old.

The 111-206 study design is presented in [Figure 4.2.1](#). All subjects who complete the 111-206 study will be eligible to receive vosoritide in the extension study 111-208 after the Week 52 visit.

Figure 4.2.1: Study Design

4.3 Study Populations

Subjects aged 0 to < 60 months old, with documented ACH confirmed by genetic testing, and who meet the study eligibility criteria will participate.

For additional criteria for selection of study population, please refer to inclusion and exclusion criteria for the protocol.

4.4 Study Dosage and Administration

In Study 111-206, sentinel subjects in Cohort 1 will receive an initial daily dose of 15 µg/kg. All available safety and PK data will be reviewed after 3 sentinel subjects reach Day 8. If the criteria for dose adjustment are met, the 3 sentinel subjects will be started on the new adjusted dose at their next scheduled visit and the remainder of the subjects in the age cohort will also be enrolled starting at the new adjusted dose. The 3 sentinel subjects for the second and third cohorts will be evaluated similarly to the sentinel subjects in the first cohort for potential dose adjustment. Additional sentinels may be added to any cohort if needed for additional safety and/or PK assessment.

4.5 Sample Size Determination

Approximately 70 subjects aged 0 to < 60 months at study entry will participate in 111-206. No formal sample size calculations were performed. The number of subjects is considered appropriate to evaluate the safety and efficacy of vosoritide in the target population.

4.6 Blinding and Randomization Methods

4.6.1 Blinding Method

This is a placebo-controlled, double-blind study. Blinding is strictly maintained during the study and a study specific masking plan describes how potentially unblinding data are handled during the lifetime of the study. The study will remain blinded until after all data has been entered, and the final database has been locked.

4.6.2 Randomization Method

The centralized randomization with stratification is managed by an external vendor, using IXRS technology.

Subjects will be enrolled into 3 age cohorts based on age at study screening starting with the eldest population. In each cohort, eligible subjects will be randomized in a 1:1 ratio to vosoritide or placebo after 3 sentinel subjects are treated. Cohorts 1 and 2 will be stratified by age. Subjects are randomized separately within each cohort in Japan.

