Appendix [25.1](#) provides details of the derivations used for each endpoint.

All efficacy endpoints will be assessed using the FAS.

Visit windows are applied for all assessments (see Section [5.4](#)) and are used to summarize the growth measures by visit.

All parameter assessments are considered for inclusion in analyses.

With the exception of AGV (see Section 14.3.2), summary tables for all growth measures including standing height/body length Z-Score, standing height/body length, upper to lower body segment ratio, body proportion ratios, other growth measures (see Section 14.3.5), BMI, BMI Z-Scores, and weight Z-Scores will include assessments at baseline, Week 26 and Week 52 from Study 111-206, and 6 months prior in Study 111-901. For subjects in Cohort 3 assessments at 3 months prior to baseline in Studies 111-206 or 111-901 will be included.

Each table will include summaries of the absolute observed measures and its change from baseline at each of these time points. The tables will summarize data separately by cohort by treatment group using format as specified in Table 5.1, Table 5.2, and Table 5.3 for Cohorts 1, 2, and 3, respectively.

ANCOVA models will be conducted for change from baseline at Week 52 in standing height/body length Z-Score, standing height/body length, AGV, and upper to lower body ratio for all cohorts overall and/or by cohort, as appropriate. Unless otherwise specified, all models will include the following baseline covariates: randomization age stratum, age at baseline, baseline AGV, and sex. Analyses of standing height/body length Z-Score, standing height/body length, and upper to lower body ratio will include their baseline as additional covariate.

For the model-based analyses, if the required assessment at Week 52 is missing but there are assessments before and after Week 52, a linear interpolation using the measurements closest to the before and after Week 52 will be used, otherwise those with no assessment after Week 52, multiple imputation by using placebo data from subjects in the same cohort (PROC MI) will be used to impute the missing values for standing height/body length and upper to lower body segment ratio at Week 52.

In addition to the primary analyses conducted on FAS, sensitivity analyses will also be conducted and are described in Section 14.2.

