24 SUMMARY OF KEY CHANGES TO STUDY SAP

Version		Affected Section	Summary of Revisions
Number	Date		
1.1	17Nov2021	Section 14.1	Option OBSMARGINS was added in the PROC MIXED procedure.
		Section 15.1.2	Definition for Algorithmic Anaphylaxis SMQ has been updated.
		Section 19	
“by cohort” was removed for box plots.
 
Box plot for maximum severity of hypersensitivity adverse events by TAb status was removed.
 
Injection site hemorrhage, injection site hematoma, injection site bruising, and injection site induration will be excluded for the box plot of maximum duration of injection site reaction adverse event by TAb status.

2.0	02Feb2022	Section 14.1	Per feedback from FDA, multiple imputation was added as imputation method if assessment at Week 52 is missing and there is no assessment after Week 52.
		Section 14.2.1	Per feedback from FDA, it was made clear that the primary analysis will be performed on randomized subjects only. “by imputation ” was added in the PROC MIXED procedure to analyze the multiple imputed data, “PROC MIANALYZE” was added to summarize results from multiple imputation.
		Section 14.2.1 & Section 14.3	Age stratum was added as a covariate in the ANCOVA model since subjects were randomized by age stratum
		Section 14.2.1	Spaghetti plots for standing height/body length Z-Score were replaced by individual line plots and line plots of mean +/- SD.
		Section 14.3.1	Line plots of mean +/- SD for standing height/body length were added.
		Section 14.3.2	Individual line plots of cumulative AGV were added.
		Section 14.3.3	Individual line plots and line plots of mean +/- SD for upper to lower body segment ratio were added.

Version		Affected Section	Summary of Revisions
Number	Date		
		Section 14.4.6	Variables for sleep study scores were updated to be clear and consistent with the data collected.
		Section 15.3	By visit was added for the tables of change in blood pressures.
		Section 16.4	Percent change from baseline was added for summary of MRI.
		Section 23	Reference of achondroplasia data was updated.

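### The ANCOVA leaves out Japan, although Japan was randomized separately in every cohort and the SAP adjusts for age stratum because it was a randomization factor

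*SAP*

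**What the plan says.** All references are to SAP version 2.0.

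- **Randomization (4.2, 4.6.2).** Allocation is 1:1 within each of three cohorts after the sentinels. On age: "Cohorts 1 and 2 will be stratified by age". Section 4.2 gives two age bands for each of those cohorts and none for Cohort 3. Section 4.6.2 then adds: "Subjects are randomized separately within each cohort in Japan".
- **Model (14.1).** Unless otherwise specified, "all models will include the following baseline covariates: randomization age stratum, age at baseline, baseline AGV, and sex". The baseline value of the endpoint is added, except for AGV, where baseline AGV already plays that part. Sections 14.2.1 and 14.3.1 to 14.3.3 repeat these covariates. The PROC MIXED code in 14.2.1 has treatment, sex and age stratum as its class variables. No Japan, region or cohort term appears. The models are to be fitted overall and/or by cohort.
- **Reason for the stratum term (Section 24, entry for version 2.0).** "Age stratum was added as a covariate in the ANCOVA model since subjects were randomized by age stratum". This entry explains a term in the current model, so it is relevant here even though it stands in a change log.
- **Sample size (4.5).** "No formal sample size calculations were performed". The total is about 70.

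**The concern.** A factor that restricts the randomization normally belongs in the analysis model. If it is prognostic and is left out, the randomization has already balanced it between arms, but the model still counts its variation as residual noise. The reported standard error is then too large, the confidence interval too wide and the test conservative.

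The SAP accepts this principle for age stratum and does not apply it to Japan. It gives no reason for the difference, and Section 22, on departures from the protocol analyses, does not mention it. What is at stake is some precision in the primary and key secondary comparisons of a small trial with no stated power margin.

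**Working it through.** **1. Numbers randomized (4.2).** The cohort minima are 27, 17 and 17, so 27 + 17 + 17 = 61. Adding 3 × 3 = 9 sentinels gives 70, which reproduces the planned total. There is no power or effect-size figure to reproduce.

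**2. Degrees of freedom, overall primary model.** With age stratum at five levels (four age bands plus Cohort 3), the parameters are: intercept 1, treatment 1, age 1, sex 1, stratum 4, baseline AGV 1, baseline Z-score 1, total 10. Residual df = 61 − 10 = 51. A Japan term makes it 50. The AGV model has one parameter fewer, so it goes from 52 to 51.

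**3. Degrees of freedom, by cohort.** Cohorts 1 and 2 each need 7 parameters (one stratum term instead of four): 27 − 7 = 20 and 17 − 7 = 10. In Cohort 3 the stratum is constant and drops out: 17 − 6 = 11.

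**4. Standard error.** If Japan explains a share R² of the residual variance of the SAP model, the standard error without the term relative to that with it is about 1/√(1 − R²), ignoring the one df:

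- R² = 0.05: 1/√0.95 = 1.026
- R² = 0.10: 1/√0.90 = 1.054
- R² = 0: 1.000

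The range of R² is an assumption. The SAP gives neither the number of Japanese children nor any sign of how Japan relates to the outcome.

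**5. Simulation check.** There were 4,000 runs per setting with N = 61. Assumed, none of it in the SAP: permuted blocks of 4, one Japan list per cohort, Japanese share p of 10, 20 or 30%, Japan shift g of 0, 0.5 or 1 residual SD, residual SD 1. Both models use the five-level stratum.

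- Absolute bias was at most 0.007 SD in either model.
- Null rejection at nominal 5% was 3.9 to 5.4% for the SAP model and 4.9 to 5.7% with Japan added. The Monte Carlo error is √(0.05 × 0.95/4000) = 0.34 percentage points.

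Power was run for an assumed effect of 0.6 SD in three settings. The implied R² is p(1 − p)g²/[1 + p(1 − p)g²].

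| p, g | Implied R² | Mean model SE, without / with Japan | Power, without / with Japan |
|---|---|---|---|
| 20%, 0.5 SD | 0.04/1.04 = 3.8% | 0.271 / 0.266 | 57.5% / 59.1% |
| 20%, 1 SD | 0.16/1.16 = 13.8% | 0.287 / 0.267 | 54.1% / 60.6% |
| 30%, 1 SD | 0.21/1.21 = 17.4% | 0.294 / 0.267 | 50.6% / 58.5% |

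The 5 to 10% range lies between the first and second rows. The null setting with p = 10% and g = 1 SD falls inside it (0.09/1.09 = 8.3%). There the mean model SE was 0.278 without and 0.268 with Japan, a ratio of 1.037. That is close to the formula's 1/√(1 − 0.083) = 1.044.

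**The case against.** The best defence is that nothing in the SAP shows Japan to be prognostic. The outcome is a within-child change in an age- and sex-standardized score, already adjusted for baseline Z-score, baseline AGV, age and sex, so little may be left for country to explain. The SAP says stratified for age but only randomized separately for Japan. The planned test is valid or slightly conservative, and there is no power target to miss.

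Most of this stands, and it limits the point to precision. It does not remove the inconsistency: a separate list is a restriction on allocation whatever it is called, and the SAP's stated reason for adjusting does not depend on the factor being prognostic.

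The by-cohort models are a fair further objection. With about 10 residual df in Cohort 2, another and possibly sparse term is a real cost.

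Two stronger readings are tempting.

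- **Biased estimate or inflated type I error.** A reader might infer either from the missing term. Neither follows, and the simulation shows neither.
- **Loss of Cohort 3.** A reader might infer that Cohort 3, having no age stratum, drops out of the overall model because PROC MIXED omits records with a missing class value. That would be 17 of 61, or 28%. The SAP does not support this. Section 14.2.1 sets the population as all randomized subjects. Section 4.2 and Tables 5.1 to 5.3 describe four age bands plus one undivided Cohort 3. The loss needs a blank code that the SAP nowhere states. Under the natural five-level coding no one is lost, and the differences between cohorts are absorbed. What remains is that this coding is not written down.

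**Conclusion.** The point holds as a modest one about precision and consistency. The SAP randomizes by Japan within cohort, adjusts for age stratum because it was a randomization factor, and leaves Japan out without explanation. Under the assumption that Japan explains 5 to 10% of residual variance, the standard error is about 2.6 to 5.4% larger than it needs to be; if Japan is not prognostic, the loss is nil. The simulated power losses of 6.5 and 7.9 points belong to a 1 SD shift with 20 to 30% Japanese children, beyond that range, and should not be quoted as expected. The 28% loss of subjects should not be quoted as the size of the problem. The SAP does not say how many children were Japanese or whether the Japanese lists were also stratified by age, so only a range can be given.

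**What to change.** - **Overall models, primary and key secondary endpoints:** add a Japan yes/no term in 14.1, 14.2.1 and 14.3.1 to 14.3.3. If it is left out, state why.
- **Age stratum:** define it in 14.1 as five levels for the overall model, namely the four age bands and Cohort 3 as its own level. State that it drops out of the Cohort 3-only model.
- **By-cohort models:** decide before unblinding whether each carries the Japan term, using blinded total counts of Japanese children per cohort. A rule that depends on how those children split between arms should not be used, because the split is known only after unblinding.

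The cost is one model term, a coding line and one degree of freedom in each overall model (51 to 50 for the primary with 61 randomized). No new data should be needed, since the allocation lists are held centrally in the IXRS.

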4.7 Interim Analysis

No formal interim futility/efficacy analyses are planned. Two informal interim analyses including data from both Studies 111-206 and 111-208 were performed for selected domains: one for New Drug Application (NDA) to Food and Drug Administration (FDA) and marketing authorization applications (MAA) to European Medicines Agency (EMA), dated 18 December 2019, and another for Japan New Drug Application (JNDA), dated 11 November 2020. For these analyses, subjects remained blinded and no efficacy data was analyzed for the randomized subjects nor post baseline listings except for serious adverse events.

In addition to safety and PK monitoring by BioMarin Personnel, an independent data monitoring committee (DMC) will act in an advisory capacity to BioMarin to monitor subject safety and PK of subjects who participate in the study. A DMC review will occur to evaluate all available safety and PK data after the sentinel subjects complete 12 weeks of dosing, and DMC will make recommendations for stopping or continuing the study, and endorse dose adjustments if needed, based on pre-specified criteria. DMC data review meetings occur approximately every 6 months during the course of the study.

5 GENERAL ANALYSIS CONSIDERATIONS

The analyses described in this final SAP are based on Amendment 2 of the protocol (date: 08 February 2019).

Individual subject data that is reflected in data summaries will be provided in listings. Unless otherwise specified, all listings will be by cohort, by sentinel/randomized subjects, by treatment group, and ordered by subject number, where subject number includes the site number.

Unless otherwise specified, summary tables for efficacy variables will use format in [Table 5.1](#), [Table 5.2](#), and [Table 5.3](#) for Cohorts 1, 2, and 3, respectively. Summary tables for safety variables will be separated by cohort and overall by treatment group using format in [Table 5.4](#).

Table 5.1: Format for Efficacy Summary Analyses for Cohort 1

Sentinel	Randomized						All Vosoritide Treated*		
	Vosoritide			Placebo					
	≥ 24 to < 36 months	≥ 36 to < 60 months	Over all	≥ 24 to < 36 months	≥ 36 to < 60 months	Over all	≥ 24 to < 36 months	≥ 36 to < 60 months	Over all

*All vosoritide treated includes sentinel subjects and randomized subjects who received vosoritide.

Table 5.2: Format for Efficacy Summary Analyses for Cohort 2

Sentinel	Randomized						All Vosoritide Treated*		
	Vosoritide			Placebo					
	≥ 6 to < 15 months	≥ 15 to < 24 months	Over all	≥ 6 to < 15 months	≥ 15 to < 24 months	Over all	≥ 6 to < 15 months	≥ 15 to < 24 months	Over all

*All vosoritide treated includes sentinel subjects and randomized subjects who received vosoritide.

Table 5.3: Format for Efficacy Summary Analyses for Cohort 3

Sentinel	Randomized		All Vosoritide Treated*
	Vosoritide	Placebo	

*All vosoritide treated includes sentinel subjects and randomized subjects who received vosoritide.

Table 5.4: Format for Safety Summary Analyses for Cohort 1*

Sentinel	Randomized		All Vosoritide Treated**
	Vosoritide	Placebo	

* Cohort 2, Cohort 3, and Overall will have the same format as Cohort 1.

**All vosoritide treated includes sentinel subjects and randomized subjects who received vosoritide.

Baseline growth measures (other than AGV, baseline AGV is defined in Section 14.3.2) and baseline weight are those assessed on Day 1 of dosing, regardless of timing relative to dosing. (Note: If no assessments are available, then the baseline assessment will be the last non-missing assessment prior to Day 1). Baseline assessments are the last non-missing on-study assessments prior to administration of study treatment. Change from baseline is calculated as: (post-baseline value – baseline value); Percent change from baseline is calculated as: $(\text{[post-baseline value – baseline value]}/\text{baseline value}) \times 100$.

The screening visit will not be presented in descriptive summaries over time. When the analysis windows have been applied (see Section 5.4), data collected at the screening visit may be included in the baseline assessment. All assessments will be listed, but only those assessments assigned to visits according to the windows applied (see Section 5.4) will be summarized in tables or graphically. Exceptions to this are summaries of the worst post-baseline laboratory data in shift tables where all assessments are considered.

Unless otherwise specified, summary statistics n, mean, standard deviation (SD), median, 25th and 75th percentile, minimum, and maximum will be provided for numerical variables. The mean, 25th percentile, median, 75th percentile, and estimates of precision (e.g. SD, confidence interval) will be displayed to one more decimal place than the collected data. Minimum and maximum values will be presented to the same decimal places as the collected data. The number of decimal places to which endpoints are reported follow the project programming standards.

Number and percentage will be provided for categorical variables. When summarizing categorical data, for mutually exclusive categories, the sum of the individual categories, including a separate “Missing” category, should equal 100%. Unless otherwise specified, if categories have no data, then they will not be displayed.

All statistical analyses will be performed using SAS® version 9.4 or a later release (SAS Institute, North Carolina, USA) and results be presented in the form of tables, listings, and graphs (TLGs). All statistical analyses, including dataset creation and output generation, will

be performed by Biostatistics and Statistical Programming personnel of BioMarin's Biometrics department.

5.1 Analysis Populations

5.1.1 Full Analysis Set

The Full Analysis Set (FAS) is defined according to the intent-to-treat principle and includes all enrolled sentinel and randomized subjects with a signed informed consent. The FAS will be the main analysis population for summaries and/or analyses described in the SAP, including but not limited to summaries and/or analyses of demographics, baseline characteristics, dispositions, and all efficacy endpoints.

All listings, excluding screen failures, will be produced on the FAS.

